## Statistical Analysis Plan

Sponsor Name: Nitto Denko Corporation  
Sponsor Protocol ID: ND-L02-s0201-005

### 7.6.9 Impact of COVID-19 Pandemic

The impact of COVID-19 pandemic on subject participation in the study will be summarized by treatment arm (including a total column) and visit with the number and percentage of subjects whose planned study visit was not performed, partially performed, performed by telephone visit, or performed outside of the protocol-specified window. In addition, a summary of subjects who early terminated study treatment or the study due to COVID-19 also will be provided. The subject-level listing will be provided and it will include any alternative procedures used to collect data per the eCRF.

Listing of protocol deviations due to COVID-19 will also be provided.

### 7.7 Interim Analysis

No formal interim analyses are planned for this study.

## 8. Changes in Planned Analysis

The following changes from protocol specified statistical analyses are made in this SAP.

Section 3.2 and 7.5.2.4 The efficacy endpoint Time to first acute IPF exacerbation has been updated to Time to first acute IPF exacerbation and death to avoid dependent censoring.

Section 7.5.2.1, 7.5.2.2, 7.5.2.3, and 7.5.5 Analysis of change from baseline in FVC, DLco, HRCT QLF, [REDACTED] will be using random coefficient model instead of ANCOVA. The random coefficient model will handle missing data by making use of all available data include subjects with missing data and no missing value will be imputed.

Section 7.5.3 Sensitivity analysis of FVC will use multiple imputation instead of ANCOVA without missing value imputation.

[REDACTED]

[REDACTED]

[REDACTED]

[REDACTED]

**Statistical Analysis Plan**

Sponsor Name: Nitto Denko Corporation  
Sponsor Protocol ID: ND-L02-s0201-005

[REDACTED]

[REDACTED]  
[REDACTED]  
[REDACTED]  
[REDACTED]

## Appendices

### Appendix 1: GAP Algorithm for IPF Stage and Predicted Mortality

GAP IPF stage for each subject will be derived by summing the points in each of the following categories for each randomized subject:

Gender	Points
Male	0
Female	1
Age	
≤60	0
61-65	1
>65	2
Baseline FVC, % Predicted	
>75	0
50-75	1
<50	2
Baseline DLco*, % Predicted	
>55	0
36-55	1
≤35	2
Not Performed	3

\*Corrected for hemoglobin

IPF stage for each subject will be assigned based on the total points as follows:

Sum of Points	IPF Stage
0-3	I
4-5	II
6-8	II

Risk of mortality will be derived using the following algorithm:

Step 1: Calculate S

$$S = [0.337 (\text{GENDER}) - 0.015 (\text{FVC} - 68.464) + 0.092 (\text{AGE1} - 67.676) - 0.052 (\text{AGE2}) + 2.237 (\text{DLco1}) + 0.024 (\text{DLco2})] \times 0.909$$

Where:

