## Statistical Analysis Plan

Sponsor Name: Nitto Denko Corporation  
Sponsor Protocol ID: ND-L02-s0201-005

- weight (kg);
- height (cm);
- body mass index (kg/m^2) [calculated as (weight/height) where weight is in kg and height is in m];
- systolic blood pressure (mmHg);
- diastolic blood pressure (mmHg);
- body temperature (°C);
- pulse rate (beats/min);
- respiratory rate breaths (breaths/min);
- pulse oximetry (SPO2) (%);
- forced vital capacity (FVC) in L;
- percent predicted FVC (%);
- forced expiratory volume in 1 second (FEV1) in L;
- percent predicted FEV1 (%);
- ratio of FEV1/FVC;
- diffusion capacity of the lung for carbon monoxide (DLco) ;
- percent predicted DLco (%);
- hemoglobin corrected DLco;
- hemoglobin corrected percent predicted DLco (%);
- [REDACTED]
- duration of IPF since diagnosis to start of study treatment (months)
  - calculated as (first dose date-initial IPF diagnosis date+1)/30.4375
- GAP IPF Risk of Mortality: The risk of mortality (1-, 2-, and 3-year risk) will be derived based on baseline data at the start of the treatment period using the Gender, Age, and Physiology (GAP) methodology described in Ley et al, 2012 ([Appendix 1](#));

The total counts and percentages of subjects will be presented for the categorical variables of:

- gender;
- childbearing potential for females
- race;
- ethnicity;
- BMI group [Underweight (below 18.5); Normal (18.5 - 24.9); Overweight (25 - 29.9); Obese (30 and above)]
- smoking history(yes/no)
  - If smoking history is yes, active smoker(yes/no)
- background standard of care (nintedanib, pirfenidone, none);

■

■

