## Statistical Analysis Plan

Sponsor Name: Nitto Denko Corporation  
Sponsor Protocol ID: ND-L02-s0201-005

- BMI (<30 vs. ≥30)
- GAP IPF Stage (I vs. II vs. III)
- Duration of IPF since diagnosis to start of study treatment (≤1 vs. 1<-2 vs. 2<-3 vs. 3<-4 vs. ≥4 year)
- Subjects who adhere to the protocol schedule vs. subjects who missed at least one treatment but continued treatment after the interruption vs. early terminated subjects (subjects did not miss any treatment before early termination)
- COVID-19 vaccination (not vaccinated vs. vaccinated prior to treatment start vs. vaccinated while on treatment)

More subgroup analysis may be done ad-hoc given feasible data support.

No adjustment to the significance level for testing will be made. For each subgroup level, the analysis will be as described in 7.5.2 except for subgroup analysis of standard of care, the standard of care covariate will be removed from the analysis model.

If there are less than 10 subjects across both treatment arms in comparison in a subcategory then only descriptive summaries will be provided.

Forest plots will be provided for the secondary efficacy analysis. For rate of decline in FVC (L) or FVC (%FVC) from baseline to Visit 14, the estimated mean slope difference and 95% CI will be summarized and presented on the forest plot for each subgroup category as well as the overall ITT population. For change from baseline in FVC (L), percent predicted FVC (%FVC), DLco corrected for hemoglobin, DLco not corrected for hemoglobin, and quantitative HRCT variables (as described in 3.4.3), estimated means difference and 95% CI will be summarized and presented on the forest plot for each subgroup category as well as the overall ITT population. If the model does not converge then only descriptive summaries will be presented.

For time to event analysis described in section 7.5.2.4 and 7.5.2.5, for each subgroup level of a factor, the hazard ratio (HR) and 95% CI will be calculated from a Cox proportional hazards model that includes treatment and presented on a forest plot. If there are too few events available for a meaningful analysis of a particular subgroup (less than 10 events across both treatment arms in comparison in a subcategory), the HR and 95% CI will not be created for the subgroup and only descriptive summaries (number of event and proportion of subjects with events) will be provided.

[REDACTED]

[REDACTED]

[REDACTED]

[REDACTED]

[REDACTED]

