### Statistical Analysis Plan

Sponsor Name: Nitto Denko Corporation  
Sponsor Protocol ID: ND-L02-s0201-005

1) GENDER =

- a. 0.293 if the patient is male
- b. -0.707 if the patient is female

2) FVC = FVC, % predicted at baseline

3) AGE1 = patient's age (years)

4) AGE2 = refer to the table below. Enter the value of AGE2 that corresponds to the patient's age.

AGE	AGE2	AGE	AGE2	AGE	AGE2	AGE	AGE2
≤50	0	60	0.236	70	6.345	80	22.043
51	0	61	0.408	71	7.625	81	23.739
52	0	62	0.648	72	9.009	82	25.435
53	0	63	0.968	73	10.481	83	27.130
54	0	64	1.378	74	12.027	84	28.826
55	0	65	1.890	75	13.632	85	30.522
56	0.002	66	2.516	76	15.280	86	32.217
57	0.015	67	3.266	77	16.959	87	33.913
58	0.051	68	4.153	78	18.652	88	35.609
59	0.121	69	5.183	79	20.348	89	37.304

5) DLco1 =

- a. 0.921 if the subject could not do the DLco test
- b. -0.079 if the subject could do the DLco test

6) DLco2 =

- a. -50.549 if the subject could not do the DLco test
- b. (49.451 - the subject's baseline DLco, % predicted) if the subject could do the test

Step 2: Calculate risk using S:

$$1\text{-year risk} = 100 \times [1 - \exp(-\exp(S) \times 0.225)]$$

$$2\text{-year risk} = 100 \times [1 - \exp(-\exp(S) \times 0.486)]$$

$$3\text{-year risk} = 100 \times [1 - \exp(-\exp(S) \times 0.768)]$$

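### SAP Appendix 1 gives women the extra GAP point but gives men the higher predicted mortality, and its stage table as extracted has no Stage III

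*SAP*

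**What the plan says.** SAP Appendix 1 derives two quantities from the same four items (sex, age, % predicted FVC, % predicted DLco).

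- **Stage.** "GAP IPF stage for each subject will be derived by summing the points in each of the following categories for each randomized subject". The sex rows read Male 0, Female 1. Then "IPF stage for each subject will be assigned based on the total points as follows": 0-3 is I, 4-5 is II and, as extracted, 6-8 is also II.
- **Mortality risk.** "Risk of mortality will be derived using the following algorithm": a score S that contains +0.337 x GENDER, the whole multiplied by 0.909. GENDER is "0.293 if the patient is male" and, with a minus sign, "0.707 if the patient is female". The 1-, 2- and 3-year risks all rise with S.

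Both quantities are used. In SAP 7.4, "The risk of mortality (1-, 2-, and 3-year risk) will be derived based on baseline data at the start of the treatment period", and stage is listed there as a categorical baseline variable; both are tied to the same cited GAP publication. SAP 7.5.4 makes stage a subgroup factor for the secondary efficacy endpoints: "GAP IPF Stage (I vs. II vs. III").

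**The concern.** A points score and a formula built from the same risk model may differ in coarseness, but not in the direction of an item. Here the points make female sex the worse category and the formula makes male sex the worse one. A programmer who follows the appendix literally will produce one wrong output: the stage if the points are reversed, or the predicted risk if the GENDER values are. Double programming from the same specification would not reveal it.

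The stage table raises a second question. If 6-8 points really is labelled II, no total leads to Stage III, and one of the three planned subgroup levels is empty by construction.

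SAP 7.5.1 states that there is no primary efficacy endpoint, so the secondary endpoints carry the efficacy evidence, and GAP stage is one of the prespecified factors for judging its consistency.

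**Working it through.** **Inputs (all SAP Appendix 1).** Points: male 0, female 1; age <=60, 61-65, >65 = 0, 1, 2; FVC >75, 50-75, <50 = 0, 1, 2; DLco >55, 36-55, <=35 = 0, 1, 2, not performed 3. Formula:

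S = [0.337 GENDER - 0.015(FVC - 68.464) + 0.092(AGE1 - 67.676) - 0.052 AGE2 + 2.237 DLco1 + 0.024 DLco2] x 0.909

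1-, 2- and 3-year risk = 100 x [1 - exp(-exp(S) x h)], with h = 0.225, 0.486, 0.768.

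**Step 1: sex effect in the formula.** With everything else equal, S(man) - S(woman) = 0.337 x (0.293 + 0.707) x 0.909 = 0.3063. The hazard ratio, man to woman, is exp(0.3063) = 1.36.

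**Step 2: direction of every item.**

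| Comparison | Formula hazard ratio | Points | Same direction? |
|---|---|---|---|
| Age 66 vs 60 | 1.48 | 2 vs 0 | yes |
| FVC 60% vs 80% | 1.31 | 1 vs 0 | yes |
| DLco 45% vs 60% | 1.39 | 1 vs 0 | yes |
| DLco 33% vs 45% | 1.30 | 2 vs 1 | yes |
| DLco not performed vs 33% | 1.77 | 3 vs 2 | yes |
| Man vs woman | 1.36 | 0 vs 1 | **no** |

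S rises at every year of age from 40 to 80, the eligible range. The sex effect is about as large as one band of FVC or DLco.

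**Step 3: a matched pair** at age 70 (AGE2 = 6.345), FVC 80%, DLco 45%. The terms other than sex are -0.1730 + 0.2138 - 0.3299 - 0.1767 + 0.1068 = -0.3591 (summed before rounding).

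- Man: S = (0.0987 - 0.3591) x 0.909 = -0.2366; risks 16.3%, 31.9%, 45.5%. Points 0 + 2 + 0 + 1 = 3, Stage I.
- Woman: S = (-0.2383 - 0.3591) x 0.909 = -0.5430; risks 12.3%, 24.6%, 36.0%. Points 1 + 2 + 0 + 1 = 4, Stage II.

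**Step 4: score profiles.** With DLco performed, as eligibility requires, there are 3 x 3 x 3 = 27 age-FVC-DLco combinations. These are combinations, not patients. Seven of them total 3 and three total 5.

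- As extracted, the woman is a stage above the man in 7 of 27 (total 3). With 6-8 labelled III it is 7 + 3 = 10. The reverse never occurs, although the formula gives the man the higher risk in all 27.
- Over the 54 sex-specific profiles, relabelling 6-8 alone changes the stage of 5; turning the sex points to the formula's direction alone changes 14; both together change 19.

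**Step 5: share of subjects, under assumptions.** The documents give only eligibility limits, so all distributions here are assumed: mean age 62-72, 60-80% men, mean FVC 72-80%, mean DLco 44-52%, SDs of 7 years, 15% and 13% (central) or smaller and larger sets, items independent, truncated to age 40-80, FVC >=45%, DLco >=30%.

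- If the formula's direction is right, correcting label and sex points changes the stage of about 22-47% of subjects with the central SDs (22-29% at mean age 62, 43-47% at 72), or 21-52% with the SDs also varied.
- The label alone moves about 0.1-3.4%.

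**Step 6: the other branch.** If the points table is right, stage changes only through the label, but every predicted risk is wrong. Swapping the two GENDER values multiplies each woman's hazard by 1.36 and divides each man's by 1.36; the example man's 1-year risk falls from 16.3% to 12.3%. Reversing the sign of the 0.337 coefficient instead gives exp(2 x 0.337 x 0.707 x 0.909) = 1.54 for women and exp(-2 x 0.337 x 0.293 x 0.909) = 0.84 for men, and 13.8% for that man.

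**The case against.** The sex arithmetic is not in dispute. The fair objections concern weight.

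- **The label rests on one machine-read cell.** Losing an I from III is a typical PDF-reading fault, and SAP 7.5.4 makes the intended levels plain. That stands, so this part is only a check of the original. Its effect is also small. Under the step 5 assumptions, Stage III holds at most about 6.7% of subjects even after both corrections, roughly 5 of the 80 in an active-versus-placebo comparison. SAP 7.5.4 then applies: "If there are less than 10 subjects across both treatment arms in comparison in a subcategory then only descriptive summaries will be provided".
- **The simulated shares are soft.** They hold only if the formula's direction is the right one, and they assume independent items. With an assumed correlation of 0.5 between FVC and DLco, one mid-range case falls from 38.6% to 34.2%. This also stands: the shares are illustrative, and the finding does not depend on them.
- **The reach is narrow.** SAP 7.4 plans no significance tests on baseline data, GAP stage is one of seven listed subgroup factors with no multiplicity adjustment, and both quantities can be re-derived from collected data. This limits the severity but does not remove the error.

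A reading fault does not plausibly explain the sex conflict: it appears in two labelled table rows and two labelled formula values, which would have to be misread consistently.

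**Conclusion.** The concern holds. Appendix 1 contradicts itself on sex: the points favour men, the formula favours women, and the formula's sex effect is a hazard ratio of 1.36. This follows from the printed values alone and needs no assumption. Either GAP stage or GAP predicted mortality will be wrong if programmed as written; the documents do not settle which. The missing Stage III row holds for the text as extracted and is conditional on the original PDF.

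The error should be fixed, but its reach is bounded. It affects the baseline GAP outputs and the GAP-stage subgroup analyses. It does not touch the primary safety endpoints or the documented overall ITT analyses. How many of the approximately 120 subjects would change stage cannot be fixed from the documents.

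**What to change.** In SAP Appendix 1:

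1. Check the sex points and the GENDER term against the cited GAP source and correct whichever is reversed. Take the corrected values from the source rather than choosing between swapping values and changing a sign, since these give different risks. Afterwards, the sex with the extra point must also be the one with the higher formula risk.
2. Confirm the 6-8 row in the original PDF. If it reads II, label it III to match SAP 7.5.4.
3. Derive the SAP 7.4 baseline stage and risk and the SAP 7.5.4 subgroup from the corrected appendix. Stage III stays descriptive wherever the existing fewer-than-10 rule applies.

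The cost is one or two table cells, or the GENDER term, plus one look at the source and one at the PDF. No new data or analyses are needed, and nothing is traded away.

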### Statistical Analysis Plan

Sponsor Name: Nitto Denko Corporation  
Sponsor Protocol ID: ND-L02-s0201-005

1) GENDER =

- a. 0.293 if the patient is male
- b. -0.707 if the patient is female

2) FVC = FVC, % predicted at baseline

3) AGE1 = patient's age (years)

4) AGE2 = refer to the table below. Enter the value of AGE2 that corresponds to the patient's age.

AGE	AGE2	AGE	AGE2	AGE	AGE2	AGE	AGE2
≤50	0	60	0.236	70	6.345	80	22.043
51	0	61	0.408	71	7.625	81	23.739
52	0	62	0.648	72	9.009	82	25.435
53	0	63	0.968	73	10.481	83	27.130
54	0	64	1.378	74	12.027	84	28.826
55	0	65	1.890	75	13.632	85	30.522
56	0.002	66	2.516	76	15.280	86	32.217
57	0.015	67	3.266	77	16.959	87	33.913
58	0.051	68	4.153	78	18.652	88	35.609
59	0.121	69	5.183	79	20.348	89	37.304

5) DLco1 =

- a. 0.921 if the subject could not do the DLco test
- b. -0.079 if the subject could do the DLco test

6) DLco2 =

- a. -50.549 if the subject could not do the DLco test
- b. (49.451 - the subject's baseline DLco, % predicted) if the subject could do the test

Step 2: Calculate risk using S:

$$1\text{-year risk} = 100 \times [1 - \exp(-\exp(S) \times 0.225)]$$

$$2\text{-year risk} = 100 \times [1 - \exp(-\exp(S) \times 0.486)]$$

$$3\text{-year risk} = 100 \times [1 - \exp(-\exp(S) \times 0.768)]$$

**Statistical Analysis Plan**

Sponsor Name: Nitto Denko Corporation  
 Sponsor Protocol ID: ND-L02-s0201-005

[figure not shown]
**Appendix 2: Schedule of visits**

Visit	Screening a		Treatment Period					EOT	Follow-Up		
	1a	1b	2	3	4	5, 7, 9, 11, 13 (Simple tests)	6, 8, 10, 12 (Detailed tests)	14 (or ET)	15	16	
Week	-6 to -1		0	2	4	6, 10, 14, 18, 22	8, 12, 16, 20	24 (2 wk postdose)	28 (4 wk post V14/ET)	34 (10 wk post V14/ET)	
Study Day	-42 to -7		1	2	15	29	43, 71, 99, 127, 155	57, 85, 113, 141	169	197	239
Allowable Window (days) b					± 4	± 7	± 7	± 7	± 7	± 7	± 7
Study Procedure											
Informed Consent	X c										
Eligibility	X	X	X								
Demographics and baseline characteristics	X										
Medical history	X										
Adverse events	X d	X	X	X e	X	X	X	X	X	X	X
IPF history and previous treatments	X										
Prior medications	X										
Concomitant medications	X d	X	X	X e	X	X	X	X	X	X	X
Physical examination (complete)	X							X			
Physical examination (abbreviated) f		X	X								
Height	X										
Weight	X							X			
12-lead ECG	X	X				X g		X			
Vital signs h	X	X	X	X	X	X	X	X	X	X	X
Chemistry	X		X		X	X		X	X		X
Hematology	X	X n	X			X		X	X	X n	X
Urinalysis	X							X			X
Pregnancy test (urine) for WCBP o	X		X			X		X	X	X	X
Serology (HCV Ab, HBsAg, HIV 1/2)	X										
SARS-CoV-2 test f	X										
Randomization			X								

### Statistical Analysis Plan

Sponsor Name: Nitto Denko Corporation  
 Sponsor Protocol ID: ND-L02-s0201-005

	Screening a		Treatment Period					EOT	Follow-Up		
Visit	1a	1b	2	3	4	5, 7, 9, 11, 13 (Simple tests)	6, 8, 10, 12 (Detailed tests)	14 (or ET)	15	16	
Week	-6 to -1		0	2	4	6, 10, 14, 18, 22	8, 12, 16, 20	24 (2 wk postdose)	28 (4 wk post V14/ET)	34 (10 wk post V14/ET)	
Study Day	-42 to -7		1	2	15	29	43, 71, 99, 127, 155	57, 85, 113, 141	169	197	239
Allowable Window (days) b					± 4	± 7	± 7	± 7	± 7	± 7	

Premedication (optional) w			X		X	X	X	X			
Study treatment			X		X	X	X	X			

Abbreviations: COVID-19 = coronavirus disease; ECG = electrocardiogram; EOT = end-of-treatment; ET = Early Termination; HBsAg = hepatitis B surface antigen; HCV Ab = hepatitis C virus antibody; HIV 1/2 = human immunodeficiency virus type 1 or 2; ICF = informed consent form; IPF = idiopathic pulmonary fibrosis; QC = quality control; SARS-CoV-2 = severe acute respiratory syndrome coronavirus 2; SOC = standard of care; V = Visit; WCBP = women of childbearing potential;

Note: Refer to Section 18.6 of the protocol for guidance on clinical trial conduct relating to COVID-19.

a Screening begins with the first Visit 1a procedure (excluding signing the ICF) and may be shorter than 42 days. If possible, plan Visit 1b and schedule the [redacted] at the time of Visit 1a. To assure that an ineligible subject does not undergo an unnecessary [redacted] ALL Visit 1a procedures MUST be completed before any Visit 1b procedures may be started. [redacted]

b Subjects should be dosed on the study day listed in the Study Schedule (± 4 days for Visit 3 or ± 7 days for Visits 4 to 13), ensuring a minimum of 7 days between each dose. Assessments not associated with study treatment infusion may be performed on days other than the dosing day for scheduling purposes, as long as they are performed before the infusion.

c The ICF should be signed before Visit 1a to allow the site to instruct the subject to withhold bronchodilator use as required for the Visit 1a PFT (see Section 11.2.2 of the protocol) [redacted]

d Adverse event and concomitant medication collection will begin 24 hours before Visit 1a.

e On Day 2, study personnel will call subjects not returning to the site to collect any AEs and concomitant medications that may have occurred after leaving the site on Day 1.

f Other abbreviated physical examinations may be performed at the discretion of the Investigator on the basis of signs or symptoms. See Section 11.1.3 for more information.

g During Visit 4 (Day 29), ECGs will be performed once, within 30 minutes after the end of the study treatment infusion.

## Statistical Analysis Plan

Sponsor Name: Nitto Denko Corporation  
Sponsor Protocol ID: ND-L02-s0201-005

h Vital signs and SpO2 will be measured at every study visit, except at Visit 2 (Days 2 and 3; subjects participating in the PK substudy will only have vital signs measured). On dosing days vital signs and SpO2 will be measured thrice: once before the study treatment infusion (if premedication is administered, vital signs should be measured after premedication), midinfusion  $\pm$  5 minutes [REDACTED] and within 15 minutes after the end of the study treatment infusion. The frequency of monitoring vital signs may be increased as warranted by clinical management. See Section 11.1.4 and Section 11.2.1 of the protocol for more information.

[REDACTED]

[REDACTED]

[REDACTED]

[REDACTED]

o A positive urine pregnancy test will be followed up with a serum pregnancy test.  
[REDACTED]

r Every effort should be made to test for SARS-CoV-2 virus or viral antigen at Visit 1a if testing is available. The test used should have regulatory approval for marketing and sample collection should be performed per the assay's specifications. Depending on the site and its location, options for subject testing may vary. Refer to Section 8.3.3 of the protocol for guidance on SARS-CoV-2 testing.

[REDACTED]

[REDACTED]

w Subjects may be premedicated to mitigate the risk of infusion-related reactions at the discretion of the Investigator (see Section 18.5 of the protocol).

[figure not shown]
**Statistical Analysis Plan**

[figure not shown]
Sponsor Name: Nitto Denko Corporation  
Sponsor Protocol ID: ND-L02-s0201-005

[figure not shown]

[figure not shown]
**Appendix 3: FVC and %FVC Baseline Determination**

[figure not shown]
The baseline for FVC and %FVC will be determined as per the   Specification.

[figure not shown]

[figure not shown]

[figure not shown]

[figure not shown]

[figure not shown]

[figure not shown]

[figure not shown]

[figure not shown]

[figure not shown]

[figure not shown]

...the first of these is the fact that the ...

...the second of these is the fact that the ...

...the third of these is the fact that the ...

...the fourth of these is the fact that the ...

...the fifth of these is the fact that the ...

...the sixth of these is the fact that the ...

...the seventh of these is the fact that the ...

...the eighth of these is the fact that the ...

...the ninth of these is the fact that the ...

...the tenth of these is the fact that the ...

...the eleventh of these is the fact that the ...

...the twelfth of these is the fact that the ...

...the thirteenth of these is the fact that the ...

...the fourteenth of these is the fact that the ...

...the fifteenth of these is the fact that the ...

...the sixteenth of these is the fact that the ...

...the seventeenth of these is the fact that the ...

[figure not shown]
...the eighteenth of these is the fact that the ...

[figure not shown]
The first part of the document discusses the importance of maintaining accurate records of all transactions. It emphasizes that every entry, no matter how small, should be recorded to ensure the integrity of the financial data. This includes not only sales and purchases but also expenses, income, and transfers between accounts.

[figure not shown]
Next, the document outlines the process of reconciling bank statements with the company's internal records. This step is crucial for identifying any discrepancies and ensuring that the books are balanced. It involves comparing the bank's record of transactions with the company's ledger and investigating any differences.

[figure not shown]
The document also covers the preparation of financial statements, including the balance sheet, income statement, and cash flow statement. It provides guidance on how to present this information clearly and accurately, following the relevant accounting standards and regulations.

[figure not shown]
Finally, the document discusses the importance of regular audits and reviews. It explains how these processes can help identify potential errors, fraud, or areas for improvement in the company's financial management. It also touches on the role of external auditors and the importance of transparency in financial reporting.

[figure not shown]

[figure not shown]

[figure not shown]

[figure not shown]

[figure not shown]

[figure not shown]

[figure not shown]

[figure not shown]

[figure not shown]

[figure not shown]

